NICE National Institute for Clinical Excellence

NISCHR National Institute for Social Care & Health Research

PCT Primary Care Trust

R&D Research and Development

REC Research Ethics Committee

SAE Serious Adverse Event

SAIL Secure Anonymised Information Linkage Databank

DATABANK

SEWTU South East Wales Trials Unit

SOP Standard Operating Procedure

T1D Type 1 Diabetes

TMF Trial Master File

TMG Trial Management Group

Page 7

1 Amendment History

Amendment No.	Protocol version no.	Date issued	Author(s) of changes	Details of changes made

2 Synopsis

Short title	Investigating the pathway of type 1 diabetes in childhood presenting in Primary Care
Acronym	
Internal ref. no.	
Study design	Case control study using the SAIL databank and the Brecon group database
Study participants	No direct participation with individuals
Planned sample size	Approx 400
Follow-up duration	Not applicable
Planned study period	November 2015 – October 2016
Primary objective	To investigate if there are any factors which may facilitate an opportunity for earlier diagnosis in Primary Care of children with type 1 diabetes
Secondary objectives	To investigate the risks of presenting in diabetic ketoacidosis (DKA)
Primary endpoint	Not applicable
Secondary endpoints	Not applicable
Interventions	Not applicable

Page 9

3 Study summary

The aim of the research is to get a better understanding of the pathway to diagnosis of type 1 diabetes (T1D) in childhood. By exploring the number and reason for children's appointments with their GP, prior to being diagnosed with T1D, we may be able to develop ways to aid earlier diagnosis which ultimately will help to reduce the number of children who are seriously unwell with diabetic ketoacidosis (DKA) at diagnosis. DKA is a life threatening condition and the most common cause of hospitalisation and death in children with T1D. Sadly, children continue to die at presentation of T1D including in South Wales, 2 within last four years. DKA also causes significant illness with impacts on financial and medical resources. It has also been shown that children who do not present in DKA at diagnosis are less likely to have long term diabetes-related complications. Currently, the rate of DKA is unacceptably high in the UK.

Current literature suggests that there is a missed window for diagnosis and that 25% of children are still becoming very unwell, in DKA, at onset of T1D. Studies have found that almost 30% of newly diagnosed children had at least one visit with a medical practitioner prior to diagnosis and almost half had a delayed referral to secondary care. Risk factors for presenting in DKA at onset include delayed diagnosis. This study will build on these findings by undertaking an evaluation of the number of appointments, symptoms and diagnostic tests prior to diagnosis of approximately 400 children with T1D. By modelling these data with a cohort of matched children without T1D, it will be possible to ascertain any significant differences between the two cohorts and potentially identify strategies for earlier diagnoses and prevention of DKA.

Children diagnosed with T1D between 1st January 2000 and 31st December 2015 will be identified from the Brecon Group register. These data will be linked with the SAIL Databank. The SAIL analyst will anonymise the data so that no child can be identified e.g. date of birth will be removed and replaced with age at diagnosis. The SAIL analyst will also provide data from a group of children without T1D, at the ratio of 3:1, matched by age, gender and GP practice. The SAIL analyst will extract details of all of the visits that these children made to their GP over the previous 12 months. Therefore, the data will consist of a series of codes for symptom details, diagnoses, medications, tests undertaken and other illnesses or conditions. An exploration of any differences in GP consultations between those children who were in DKA at diagnosis and those who were not will also be undertaken.

4 Introduction

Background

What triggers the onset of childhood T1D is still unknown but each year in the United Kingdom (UK) approximately 26 per 100,000 children will be diagnosed with the condition (1). Although the rate of diagnosis is reported to be rising by approximately 4% per year (2), it remains a relatively rare condition in primary care. A GP, working in a large practice, might expect to see a child with new onset T1D approximately once every two years (3). Identifying the condition has been described as 'looking for the needle in the haystack' (4) due to the non-specific nature of the clinical characteristics that can often be attributed to more common childhood conditions.

Recognition of the early symptoms of T1D is critical to ensure prompt treatment in order to avoid a child presenting in DKA, a potentially life threatening condition and the most common cause of hospitalisation and death in children with T1D (5). Sadly, children continue to die at presentation of T1D including in our own region (6). DKA also causes significant morbidity with impacts on financial and medical resources (7, 8). Children who do not present in DKA at diagnosis have significantly better residual beta cell function, resulting in improved glycaemic control and a higher rate of partial remission (9) with likely longer term reductions in diabetes-related complications, so-called 'metabolic memory' (10). Currently, the rate of DKA is unacceptably high in the UK (11).

In an effort to reduce the number of children presenting in DKA at diagnosis, various educational campaigns have been carried out around the world. By increasing awareness of the symptoms of T1D through the use of posters placed in schools and health centres; the provision of capillary blood glucose meters to doctors; and visits by educators experienced in diabetes management, the rate of DKA was reported to have reduced by 64% (12) and fell from 78% to 12.5% (13). However, in Wales, a poster campaign targeting pharmacies, GP surgeries and schools did not impact on rates of DKA at diagnosis, which remained static at 25% in the year following the campaign (14).

Gaining a greater understanding of the prodrome in the months before diagnosis could provide important information to assist development of prevention strategies to reduce the rate of DKA in the future. In a systematic review, Usher-Smith (2011) found that a considerable number of children have a delayed diagnosis or are misdiagnosed and that on average children were symptomatic for over two weeks before diagnosis (15). There is some suggestion that this may be an underestimate and children can exhibit subtle symptoms for over a month before they are diagnosed (4). Early detection may be hindered due to the child appearing relatively well, presenting with non-specific symptoms or because health practitioners have "missed" opportunities to make a diagnosis (4). One in three newly diagnosed children will have been seen by a healthcare professional at least once within the preceding weeks of their diagnosis (3).

In a qualitative study, Usher-Smith explored the pathway to diagnosis with families and GPs and identified that the greatest delay to diagnosis in the appraisal interval was attributable to parents (4). Most children in this relatively small study were diagnosed at their first GP encounter but in most cases, parents had already made or suspected the diagnosis themselves. However, the small sample size and retrospective recall of events limit interpretation of these results.

By investigating a large cohort of children, a more detailed understanding of the typical pathway to diagnosis can be formed including identification of opportunities for an earlier diagnosis. This study will link the Brecon Group Register, which contains diagnostic details including date of presentation of 98% of all known cases of T1D in Wales, with GP records held within the Secure Anonymised Information Linkage (SAIL) Databank. SAIL holds extensive Welsh population data, including primary,

secondary and social care data. It provides detailed clinical and demographic anonymised information on patients, including symptoms, diagnoses, prescriptions and medical history. This wealth of data makes it easier and more cost-effective to study much larger numbers of individuals over longer periods of time than is possible using traditional methods using prospectively collected data that are uninfluenced by recall bias. By analysing patients' consultations, recorded in SAIL, over the 12 months before diagnosis of T1D, a more detailed account of the prodrome of T1D in childhood will be developed.

This will be the first large scale study of the pathway to diagnosis in primary care, giving an unprecedented detailed account of the symptoms, numbers of visits, diagnostic tests, misdiagnosis and overall presentation of children with new onset T1D. Results will also build on research (the EDDY study: Early Diagnosis of Diabetes in Youth) currently being undertaken by the applicant and two of the co-applicants funded through the National Institute for Social Care and Health Research for Patient and Public Benefit scheme. EDDY is a feasibility study designed around King's (12) successful intervention in Australia, with the aim of designing and delivering interventions for parents, GPs and practice nurses, to raise awareness of the symptoms of T1D to prevent presentation in DKA at diagnosis. This study will identify whether there are additional opportunities to promote an earlier diagnosis, which may require interventions different or additional to those undergoing preliminary evaluation in EDDY.

Research questions

- 1. Are there factors (number and reasons for consultations, socio-demographic factors, past medical history), or combinations of factors, that are associated with a new diagnosis of T1D, as compared to children presenting with other acute conditions in the 12 months before diagnosis?
- 2. Are there differences in the patient pathway (12 month period before diagnosis), as recorded in their medical records, between patients presenting with newly diagnosed T1D who experience DKA, and those who do not experience DKA around the time of diagnosis?

5 Study objective(s)

The ultimate aim of this research is to promote earlier diagnosis of type 1 diabetes (T1D) in childhood to reduce the risk of DKA at presentation by better understanding the pathway to diagnosis through analysis of the number and reason for appointments of the child with their Primary Care Team before diagnosis and any tests conducted at these times.

Primary objective

 To investigate if there are any factors that are associated with a new diagnosis of T1D in childhood, compared to a matched group of controls without T1D, during the 12 months preceding diagnosis.

Secondary objectives

 To investigate if there are any risks associated within the patient pathway in the 12 months preceding diagnosis between children who presented in DKA or not in DKA at diagnosis.

6 Study design

This is a case control study of a linked dataset (SAIL databank and Brecon Group database). Data from all children (15yrs and below) diagnosed with type 1 diabetes between 1st January 2000 to 31st December 2015 will be linked with the SAIL databank.

An anonymised data set will be created by the SAIL research analyst. This will include a cohort of matched controls who do not have T1D identified through the SAIL databank at a ratio of 3:1. The resulting dataset will contain all GP consultation records in the 12 months prior to diagnosis for children diagnosed with T1D, those diagnosed in DKA and a matched cohort of children without T1D.

Initial analysis of the dataset will use data mining techniques to assess and explore the read codes attached to each GP consultation. Further analyses will assess each patient's prodrome (12 months prior to diagnosis) by analysing the number of GP visits, symptoms, duration of symptoms, tests undertaken and treatments given.

7 Centre and Investigator selection

Not applicable

8 Participant selection

The first stage of the study will involve identifying all children (i.e. those under 15yrs of age) diagnosed with T1D from 1st January 2000 to 31st December 2015 in the Brecon Group Register and categorising

them into those who presented with or without DKA at diagnosis. Extrapolations from the Welsh data suggest that there will be approximately 3500 children diagnosed with T1D in these years, with at least 90 children who presented in DKA. The SAIL research analyst will link these data with the GP dataset from the SAIL databank using first and last name, gender, date of birth, date of diagnosis, DKA status, GP and postcode (NHS number is not recorded in the Brecon Group Register). The dataset generated from this process will be anonymised using an ALF, ensuring the researchers do not have access to any personal identifiable data (e.g. age at diagnosis in DKA will be calculated using date of birth and date of diagnosis and then date of birth will be discarded). In addition, a cohort of controls presenting to their GP with acute illness but who do not have T1D will be identified from SAIL at the ratio of 3:1. This cohort will be matched to the T1D cohort by age, gender and GP practice. The resulting dataset therefore will contain all GP consultation records in the 12 months prior to diagnosis for children diagnosed with T1D, those diagnosed in DKA and a matched cohort of children without T1D. The cohort of children without T1D will be assigned a matched date to act as the time point for consultations in the previous 12 months. Children presenting with T1D (in or not in DKA at diagnosis) who cannot be matched (due to their GP data not being available in SAIL) will be compared to children presenting with T1D matched to SAIL, and any differences will be quantified.

Inclusion criteria

- All children 15yrs and under diagnosed with T1D between 1st January 2000 and 31st
 December 2015 and listed in the Brecon Group database.
- Matched controls, for those above, from the SAIL databank

Exclusion criteria

- All children over 15yrs old diagnosed with T1D
- All children diagnosed before 1st January 2000 and after 31st December 2015

9 Outcome measures

There are no primary or secondary end points for this study

10 Recruitment

This study is using routinely collected data and therefore will not be actively recruiting participants

Informed consent

Informed consent will not be sought from participants as all data is anonymised and is provided from existing datasets.

Randomisation/registration and unblinding

This is a case control study and therefore no participants will be randomised.

Screening logs

Not applicable

11 Withdrawal & loss to follow-up

Not applicable

12 Intervention

Not applicable

13 Adverse Events

Adverse Event (AE):

There are no expected AEs/SAEs.

Related Adverse Event/Serious Adverse Events:

There are no expected AEs/SAEs that could be related to the study. Therefore, there will be no formal process in place to collect AEs or SAEs for this study.

Adverse Event (AE):

Not applicable

Causality

Reporting procedures

Not applicable

14 Study procedures

This study will link two existing datasets, the Brecon Group (Welsh Paediatric Diabetes Interest Group) Register and GP records within the SAIL databank, to provide a unique and contemporary dataset of all children in Wales diagnosed with T1D in the 16 year period between 1st January 2000 and 31st December 2015 (approximately 3500), with details of the number and nature of any GP consultations they may have had in the 12 months before diagnosis. In addition, a cohort of children without T1D but matched for age, gender, location, socioeconomic class, GP and another acute illness (e.g. infection) will be identified to explore the specificity and predictive potential of variables related to development of T1D.

The first stage of the study will involve identifying all children (i.e. those under 15yrs of age) diagnosed with T1D from 1st January 2000 to 31st December 2015 in the Brecon Group Register and categorising them into those who presented with or without DKA at diagnosis. Extrapolations from the Welsh data suggest that there will be approximately 3500 children diagnosed with T1D in these years, with at least 700 children who presented in DKA. The SAIL research analyst will link these data with the GP dataset from the SAIL databank using:-

- First and last name
- Gender
- Date of birth
- Date of diagnosis
- DKA status
- GP practice
- Postcode (NHS number is not recorded in the Brecon Group Register).

The dataset generated from this process will be anonymised using an ALF, ensuring the researchers do not have access to any personal identifiable data (e.g. age at diagnosis in DKA will be calculated using date of birth and date of diagnosis and then date of birth will be discarded). In addition, a cohort of controls presenting to their GP with acute illness but who do not have T1D will be identified from SAIL at the ratio of 3:1. This cohort will be matched to the T1D cohort by:-

- Age
- Gender
- GP practice

The SAIL analyst will extract the following information:-

- All GP consultation records in the 12 months prior to diagnosis for children diagnosed with T1D
- All GP consultation records of the matched cohort of children without T1D. (This cohort will be matched on the date they presented to their GP with an acute illness. This will act as the time point for consultations in the previous 12 months.)

Within the consultation records variables will include:-

- Symptom details
- Diagnoses
- Tests undertaken
- Medication prescribed
- Co-morbidities

Demographic factors collected

- Children
 - Age at diagnosis
 - Gender
 - Deprivation quintile (based on postcode)
 - GP practices
 - List size
 - Number of GPs within the practice.

Initial analysis of the dataset will assess and explore the read codes attached to each GP consultation in the 12 months before diagnosis. The researchers will define the read codes and explore mechanisms for grouping symptoms to allow for meaningful clinical interpretation. Each patient's prodrome (the 12 months before diagnosis) will be assessed by analysing the number of GP visits, symptoms, diagnoses, tests undertaken and treatments given.

15 Statistical considerations

Randomisation

Not applicable

Sample size

As the primary purpose of this study is to seek an earlier diagnosis of T1D, the study is powered for the case-control study. Assuming a medium effect size (OR=1.5), a moderately low prevalence rate of the risk factor 30% in the control group, matching 3 controls per case and using a two sided 5% alpha and 80% power, we will require 322 children with T1D. If a total of around 390 children diagnosed with T1D were identified between 2010 and 2012 this would give the study over 90% power. A secondary aim of the study is to explore the risks associated with presenting in DKA (or not). Given that approximately 23% of children diagnosed with T1D are in DKA at diagnosis then we have 90 children in DKA and 300 not in DKA, we will not be powered to observe any small to medium effect sizes for any risk factors. This analysis will be exploratory in nature.

16 Analysis

Main analysis

The two groups will be described using summary statistics (N (%), mean (sd), median (inter-quartile range)) for the explanatory variables identified as described above. Predictors of presenting in DKA at diagnosis (using the explanatory variables identified) will be examined using a two-level logistic regression model (children within practice). Where numbers allow, variation in DKA will be accounted and corrected for at the level of general practice. Associations between the prodromes for children presenting in DKA will be examined firstly at the univariable level and significant predictors (with a P-value <0.10) retained for the multivariable model. Odds ratios (ORs) will be estimated together with 95% confidence intervals (CIs).

The quality of the matching will be examined by describing the case-mix (with respect to age, gender, co-morbidites and practice factors) of the case (T1D) and control (general population of children) groups. The two groups will be also be described to examine any differences in prevalence of presentation of such symptoms, GP visits, tests and medications in primary care. A similar analysis will be used as in the T1D analysis only using a conditional logistic regression model to account for the non-independent observation created by matching, and results again presented as ORs alongside 95% CIs.

Data storage & retention

All data will be kept for 15 years in line with Cardiff University's Research Governance Framework Regulations for clinical research. This data will be stored confidentially on password protected servers maintained on the Cardiff University Network.

17 Study closure

The end of the study will be considered as the date of the submission of the final report.

18 Regulatory issues

Ethical and research governance approval

The study will be conducted in accordance with the recommendations for physicians involved in research on human participants adopted by the 18th World Medical Assembly, Helsinki 1964 and later revisions. The study will be submitted to an NHS Research Ethics Committee (NHS REC) for approval. This is consistent with the requirements of Cardiff University who will be requested to act as the study sponsor.

Consent

Informed consent will not be sought from participants, as the data being used is anonymised and patients who contribute to the Brecon Group register provide consent for their data to be used for research purposes.

Confidentiality

The Chief Investigator and the research team will preserve the confidentiality of participants in accordance with the Data Protection Act 1998.

Indemnity

Cardiff University will provide indemnity and compensation in the event of a claim by, or on behalf of participants, for negligent harm as a result of the study design and/or in respect of the protocol authors/research team. Cardiff University does not provide compensation for non-negligent harm.

Study sponsorship

Cardiff University will act as sponsor for the study.

Funding

This study has been funded by the Novo Nordisk UK Research Foundation.

Audits & inspections

The study may be participant to inspection and audit by Cardiff University under their remit as sponsor.

19 Study management

Project team meetings and Study Management meetings

The project team meetings and SMG will consist of the Chief Investigator and the coapplicants. The role of the SMG will be to assist in the study set up by providing specialist advice, input to and comment on the study procedures and documents (protocol etc). They will also advise on the promotion and the running of the study and deal with any issues that arise. The group will meet, either face-to-face or using audio-conferencing facilities, as required throughout the course of the study. All SMG members will be required to sign up to the SEWTU SMG charter.

20 Data monitoring & quality assurance

Not applicable

SSC (Study Steering Committee)

A SSC will not be established for this study.

DMC (Data Monitoring Committee)

A DMC will not be established for this study.

21 Publication policy

The publication policy will be drafted and approved by the Study Management Group. It will state principles for publication, describe a process for developing output, contain a map of intended outputs and specify a timeline for delivery. The publication policy will respect the rights of all contributors to be adequately represented in outputs (e.g. authorship and acknowledgments) and the study to be appropriately acknowledged.

22 Milestones

Study timelines will be detailed in the Study Gantt chart.

23 References

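### The stated study size (about 400 cases, with 390 drawn from 2010–2012) does not match the 2000–2015 population of about 3500 cases that the protocol selects

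*Protocol*

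**What the plan says.** Two sets of numbers run through the protocol.

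**The small set.** Section 2 gives a planned sample size of roughly 400. Section 3 describes an evaluation of "symptoms and diagnostic tests prior to diagnosis of approximately 400 children with T1D". Section 15 derives a requirement of 322 cases (OR 1.5, 30% exposure in controls, three controls per case, two-sided 5%, 80% power) and continues: "If a total of around 390 children diagnosed with T1D were identified between 2010 and 2012", power would exceed 90%. It then applies a DKA proportion of about 23%, obtains 90 children in DKA and 300 not, and concludes that the DKA analysis is not powered for small to medium effects.

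**The large set.** The paragraph of section 3 that follows the 400 reads: "Children diagnosed with T1D between 1st January 2000 and 31st December 2015 will be identified from the Brecon Group register". Section 6 says that data from all children "diagnosed with type 1 diabetes between 1st January 2000 to 31st December 2015 will be linked with the SAIL databank". The inclusion criterion in section 8 begins "All children 15yrs and under diagnosed with T1D between 1st January 2000 and 31st" and runs to December 2015. Section 8 expects "approximately 3500 children diagnosed with T1D in these years, with at least 90 children who presented in DKA". Section 14 repeats the sentence with a different DKA count: "approximately 3500 children diagnosed with T1D in these years, with at least 700 children who presented in DKA".

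The amendment table in section 1 is empty, so both sets are current text.

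**The concern.** A sample size statement should describe the population that the eligibility criteria will yield. Here the headline size and the power paragraph describe something close to a three-year study, while the design, criteria and procedures describe a sixteen-year one. Section 8 foresees children whose GP data are not in SAIL, but it gives no linkage rate and does not use linkage loss to explain the 400.

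Two things are at stake. A reader who takes the synopsis at its word will misjudge the size of the study and the smallest association it can detect. And section 15 reaches a substantive conclusion about the secondary (DKA) objective, that it is underpowered and hence exploratory, from counts that belong to the small set.

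**Working it through.** **Inputs.** From section 15: p0 = 0.30, ψ = OR = 1.5, M = 3 controls per case, two-sided 5%, 80% power, 322 cases, 390 cases in 2010–2012, 90 in DKA and 300 not. From sections 2 and 3: 400 cases. From sections 8 and 14: 3500 cases, with at least 90 or at least 700 in DKA. Not in the protocol: the correlation φ of exposure between a case and its matched controls. I assume a range of 0 to 0.3.

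**Step 1: reproduce 322.** Exposure in cases is p1 = ψp0/(1 − p0 + ψp0) = 0.45/1.15 = 0.3913. For matched sets (Dupont's method), with q = 1 − p:

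- s = √(p1·q1·p0·q0); a = p0 + φs/p1 and b = p0 − φs/q1 are a control's exposure probabilities given an exposed and an unexposed case
- t_k = p1·C(M,k−1)·a^(k−1)·(1−a)^(M−k+1) + q1·C(M,k)·b^k·(1−b)^(M−k), for k = 1 to 3
- e(ψ) = Σ t_k·kψ/(kψ+M−k+1); v(ψ) = Σ t_k·kψ(M−k+1)/(kψ+M−k+1)²
- n = {[1.960√v(1) + 0.842√v(ψ)] / [e(ψ) − e(1)]}²

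With φ = 0.2: e(1) = 0.2950, e(1.5) = 0.3546, v(1) = 0.1444, v(1.5) = 0.1485. So n = [(0.7449 + 0.3243)/0.05963]² = 321.4, rounded up to 322. The plan's figure is reproduced, but φ = 0.2 is inferred from that match. An unmatched two-proportion calculation gives 280.

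**Step 2: precision at the two sizes.** Same method, solved for the OR that has 80% power:

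| φ | cases needed for OR 1.5 | power at 390 | detectable OR, 400 cases | detectable OR, 3500 cases |
|---|---|---|---|---|
| 0 | 279 | 91.1% | 1.41 | 1.12 |
| 0.1 | 298 | 89.3% | 1.42 | 1.13 |
| 0.2 | 322 | 86.9% | 1.44 | 1.13 |
| 0.3 | 355 | 83.6% | 1.47 | 1.14 |

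The stated power above 90% at 390 is reproduced near φ = 0 but not at the φ = 0.2 that gives 322. That is a separate point and does not alter this one.

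**Step 3: the size gap.** 3500/400 = 8.75. With three controls each, the whole study is 400 × 4 = 1600 children or 3500 × 4 = 14,000. For linkage loss alone to bring 3500 down to 400, it would have to be 1 − 400/3500 = 89%. For the primary comparison to fall below 322, fewer than 322/3500 = 9.2% of cases would have to link.

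**Step 4: the DKA counts.** 0.23 × 390 = 89.7, which is the 90 in section 15. On the full set, 0.23 × 3500 = 805. The minimum in section 14 is 700/3500 = 20%; the minimum in section 8 is 90/3500 = 2.6%. The 90 equals the count from the 390 and is out of line with a DKA proportion of about 23%.

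**Step 5: DKA power.** Assume 30% exposure in the non-DKA group and OR 1.5, so the difference is 0.3913 − 0.30 = 0.0913. Power = Φ[(0.0913 − 1.960·s0)/s1], with s0 the pooled and s1 the unpooled standard error.

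- 90 v 300: s0 = 0.0561, s1 = 0.0578, giving Φ(−0.32) = 37%; detectable OR 1.99.
- 700 v 2800: s0 = 0.01968, s1 = 0.02038, giving Φ(2.59) = 99.5%; detectable OR 1.29.

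These are register counts before linkage, and they ignore clustering by practice.

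**The case against.** The strongest reply is that the operative population is not in doubt. Every passage that says which children to take uses 2000–2015. The 2010–2012 sentence is conditional and is not an eligibility limit, and the synopsis figure carries no years and no sampling rule. The effect of OR 1.5 and the requirement of 322 do not depend on 2010–2012. More cases than required is no defect, and section 16 already commits to odds ratios with 95% confidence intervals. All of this stands, and it limits the point to the planning numbers.

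It also disposes of three stronger readings that a reader might infer:

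- *That the primary comparison is underpowered or has no stated design effect.* It has one, and 322 is exceeded with 390, 400 or 3500 cases.
- *That only about 400 cases would be extracted.* The selection text does not allow it.
- *That a larger set would turn trivial differences into findings.* The protocol sets no P<0.05 rule for conclusions; its one P threshold, 0.10, is for retaining predictors in a model.

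Could the 390 be a count after linkage? Section 15 says identified, not linked, and no linkage rate appears anywhere. Scaling the 390 up to sixteen years would be guesswork, so I do not offer a figure. In any case, linkage loss would not explain why the years differ.

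What the reply does not remove is that a stated sample size, repeated in two sections, is not the size of the study described, and that a stated conclusion about the DKA analysis follows from it.

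**Conclusion.** Wrong as written. The sizes in sections 2, 3 and 15 belong to a different case group from the one that sections 3, 6, 8 and 14 select, by a factor of about nine before linkage. The consequence for the primary comparison is misdescribed precision, with a detectable OR of about 1.41–1.47 at 400 cases against about 1.12–1.14 at 3500. These values assume 30% control exposure, three controls per case and an exposure correlation of 0 to 0.3; linkage loss would move the second range upward by an amount the protocol does not allow one to state.

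The consequence for the secondary objective is larger. Power for OR 1.5 is 37% on the section 15 counts and above 99% on 700 v 2800, under an assumed 30% exposure in the non-DKA group. It does not follow that the DKA analysis is well powered for every effect: the detectable OR at 700 v 2800 is still 1.29 before linkage loss and clustering. What follows is that the existing power statement cannot be carried over to the eligible set. The two DKA minima, 90 and 700, also need reconciling.

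**What to change.** - **Sections 2 and 3:** replace the figure of about 400 with the expected number of 2000–2015 cases, giving both the register total (about 3500) and the number expected after SAIL linkage, plus three controls per case. Label any linkage rate as an assumption.
- **Section 15, primary comparison:** remove the 2010–2012 basis. Keep 322 as the minimum for OR 1.5, state the exposure correlation assumed, and give the detectable OR at the expected linked number.
- **Section 15, DKA:** restate the expected DKA and non-DKA counts and the power on the 2000–2015 set, and revise the conclusion on power accordingly.
- **Sections 8 and 14:** reconcile the two minimum DKA counts.

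The cost is protocol wording and one recalculation. Eligibility, linkage and data extraction do not change, because the sixteen-year extraction is already planned.
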